6.1.5.4 Proportion of children referred with hypoxaemia who receive oxygen at hospital

Children with hypoxaemia (according to country's specific cut-off) who received a referral advice at Day0 and oxygen at hospital (according to hospital records) will be counted in the numerator. All children recruited will be in the denominator.

Furthermore, children with hypoxaemia who were referred and children with hypoxaemia who were referred and admitted to hospital will be summarised using all children recruited as denominator.

Additionally, the proportions will be calculated and reported using only children with hypoxaemia as denominator.

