- Proportion of children cured (defined as caregiver reported recovery from illness) at Day 7 follow-up
- Proportion of children referred by a primary care healthcare provider to a higher level of care (either to a hospital or to an inpatient part of a larger primary healthcare facility) at Day 0 consultation

Proportion of children who completed referral, as reported at day 7 follow-up
Other outcomes of interest – hypoxaemia (in intervention arms only)

- Proportion of children with severe ($\text{SpO}_2 < 90\%$), moderate ($\text{SpO}_2 90 - 91\%$) and mild hypoxaemia ($\text{SpO}_2 92 - 93\%$), adjusted for sites at high altitude
- Proportion of children with hypoxaemia (according to differing cut-offs) with severe complication
- Proportion of children with severe hypoxaemia not meeting any other clinical criteria for severe disease

- Proportion of children referred with hypoxaemia who receive oxygen at hospital

Other outcomes of interest – referral and follow-up

- Proportion of children with non-severe disease referred to a higher level of care on Day 0
- Average length of stay (in days) of children admitted to hospital
- Proportion of children attending scheduled follow-up at the same facility by Day 7
- Proportion of children presenting for unscheduled follow-up to any health facility by Day 7

Other outcomes of interest – antimicrobial prescription

- Proportion of children prescribed an antibiotic at Day 0
- Proportion of children prescribed a diagnosis-appropriate antibiotic
- Proportion of febrile children tested for malaria at Day 0
- Proportion of malaria positive children prescribed an antimalarial
- Proportion of malaria negative children prescribed an antimalarial
- Proportion of untested children prescribed an antimalarial

Sub-groups for analysis of primary and secondary outcomes:

- Age (under 2 months, 2 – 12 months, 13 – 59 months)
- Sex
- Presentation with cough / difficulty breathing

Other factors for exploratory analyses

- Additional sociodemographic characteristics urban / rural location, distance from health facility, key household indicators such as maternal age and education
- Main complaint / symptom categories (including cough / difficulty breathing, fever, diarrhoea and other) and time since onset of symptoms
- Alternative hypoxaemia cut-offs
- Healthcare provider severity classification
- Facility and health system factors – type of facility, healthcare provider qualification and previous training

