Quantitative research assistants will conduct the phone follow-up interviews using an EDC mobile application. Personally identifiable information (PII) will be used for contacting caregivers. No time window applies to Day 7 follow-up. A window of +7 days applies to Day 28 phone call attempts (Day 28 to Day 35).

Data that will be collected at Day 7 follow-up will include cure status (recovery from illness as reported by the caregiver), death and hospitalization information between Day 0 and Day 7 as

reported by caregivers. The primary outcomes on the proportion of children with severe complications by Day 7 and on the proportion of children admitted to hospital within 24 hours of the Day 0 primary care consultation as a result of a referral will be assessed based on Day 7 follow-up. Hospital name, duration of hospitalization and reason for admission will be collected for children reported to have been hospitalized to facilitate the retrospective data collection at referral hospital level.

Data collected at Day 28 follow-up will include death and hospitalization information as reported by the caregiver. The secondary outcome on the proportion of children with severe complications at Day 28 will be assessed on the basis of this interview.

Higher level of care visit

Data collection will be conducted retrospectively at all government-designated and private referral facilities within the study area, including hospitals or emergency / inpatient area of larger primary or secondary care facilities (e.g., study facilities that can admit paediatric patients). A quantitative research assistant using the EDC mobile application will collect data from referral facility records, registries and discharge summaries to document hospitalization for all children reported to have been hospitalized between Day 0 and Day 7. Personally identifiable information will be collected to cross-check the identity of the patients. Arrival date and time, basic clinical information on arrival and, if admitted, admission and discharge diagnosis, and admission duration and outcome will be collected. If available, data on oxygen saturation at admission, oxygen administration and intensive care unit (ICU) admission and duration will also be recorded.

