8.2.4 Data quality assurance and control

Quality assurance activities across all studies will be more intense during study start-up to ensure quality data practices are instituted from the start of the trial. Further details will be given in the DMP and SOPs.

All research assistants will be trained to provide information and seek written consent using the information and consent form. Separate trainings will cover all aspects of quantitative data collection and all aspects of qualitative data collection. A competency assessment using scenarios will be done before commencing field work.

Data reconciliation between the different visits of the same child will be one of the most crucial data quality activity in the pragmatic cluster RCT. Specific procedures will be developed for this purpose. To identify repeat visits of children that may re-attend the study facility where they enrolled or any other study facility during the follow-up period, participants will be given a study card (or sticker) with a unique ID number. Retrospective search for data at referral level will be restricted to facilities within the geographical area where the study is running and will be targeted to include only children reported to have attended hospital by the caregiver at follow-up and referred children lost to follow-up. The name of the referral facility will be requested during the follow-up call. If available, it should further restrict the scope of the search and the probability of negative matches when cross-checking the participant identity. Children who re-attend any study facility more than 28 days after their previous enrolment will be enrolled for the new disease episode and given a new ID number. If available, the old ID number will be recorded to facilitate linking of the different disease episodes. Data to be potentially reconciled will be flagged by automated cross-check of a set of personal identifiers. Given that

personal identifiers may not be identically recorded at each visit, fuzzy matching methods will be used to calculate a score of similarity between records and likelihood that they relate to the same child. Reconciliation of records with high similarity scores will be manually validated.

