6.1.2.6 Proportion of children who completed referral as reported at Day 7 follow-up

A referral will be considered completed if a child attended a hospital, whether he/she was admitted or not. Children will be counted in the numerator if they received a referral advice (as per definition above) and their caregiver reported to have sought care in a hospital and

the follow-up date is within 7 days of Day 0, considering a + 3 days window (10th day included). The denominator will be all children recruited.

Additionally, the proportion will be calculated and reported using only children who were referred as denominator.

Children for whom no Day7 data are available or withdrew prematurely from the study will be assumed not attending a hospital by Day7.

6.1.2.7 Proportion of children with non-severe disease referred to a higher level of care on Day 0

Children with non-severe disease who received a referral advice (as per definition above) at Day0 will be counted in the numerator. The denominator will be all children recruited. Non-severe disease will be defined in a separate document.

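### SAP 6.1.5.4 never divides oxygen receipt by the children referred with hypoxaemia, and its output cannot tell no oxygen from no hospital record

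*SAP*

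**What the plan says.** Protocol 6.4.2 lists "Proportion of children referred with hypoxaemia who receive oxygen at hospital" among the other outcomes of interest, for intervention arms only. SAP 3.1.4 repeats it.

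SAP 6.1.5.4 defines it as follows.

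- **Numerator:** children with hypoxaemia and a referral advice at Day 0 whose receipt of oxygen is documented: "oxygen at hospital (according to hospital records) will be counted in the numerator".
- **First denominator:** "All children recruited will be in the denominator".
- **Companion summaries, also over all recruited:** "Furthermore, children with hypoxaemia who were referred and children with hypoxaemia who were referred and admitted to hospital will be summarised".
- **Second denominator:** "Additionally, the proportions will be calculated and reported using only children with hypoxaemia as denominator".

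The parallel referral outcomes are treated differently. For completed referral, SAP 6.1.2.6 states: "Additionally, the proportion will be calculated and reported using only children who were referred as denominator". SAP 6.1.2.3 does the same for admission within 24 hours. SAP 6.1.6.1 and 6.1.6.2 add the matching conditional denominators for follow-up visits.

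On the source data, Protocol 8.1.1 says: "If available, data on oxygen saturation at admission, oxygen administration and intensive care unit (ICU) admission and duration will also be recorded". Protocol 8.2.4 says: "Retrospective search for data at referral level will be restricted to facilities within the geographical area where the study is running". SAP 6.1.5.4 has no rule for a record that is not found or that says nothing on oxygen. SAP 6.3 deals with children lost to follow-up or withdrawn, not with missing hospital records.

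**The concern.** The outcome's name poses a conditional question: once a hypoxaemic child has been referred, does the child get oxygen at hospital? The planned proportions answer a different one. They combine how often hypoxaemic children are referred with what happens afterwards, and referral is the step the intervention is designed to change (Protocol 6.4.2).

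The numerator also depends on documentation. A referred child who was given oxygen at a facility outside the study area, or whose record does not mention oxygen, satisfies the denominator but not the numerator. Poor record retrieval then looks the same as oxygen not being given.

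At stake is a descriptive link between referral and outcome. Protocol 6.4.2 notes that morbidity and mortality in severe disease depend heavily on hospital care, so readers are likely to use this figure when they interpret the severe-complication result.

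**Working it through.** The documents give no expected value for this outcome, so there is no planned figure to reproduce. All rates below are assumptions chosen for illustration; the structure comes from SAP 6.1.5.4.

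**Notation**

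- N = all recruited children
- H = children with hypoxaemia
- R = hypoxaemic and referred at Day 0
- O = hypoxaemic, referred, and oxygen shown in hospital records

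Planned outputs: O/N, O/H, R/N and R/H, plus the referred-and-admitted group over N and over H. Not planned: O/R.

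**Step 1. What the denominators do**

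O/H = (R/H) × (O/R), and O/N = (H/N) × (R/H) × (O/R).

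Assume 70% of referred hypoxaemic children arrive, 80% of arrivals are given oxygen, and every record is found. Then O/R = 0.70 × 0.80 = 56%, whatever the referral rate.

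| Assumed R/H | Planned O/H | O/R |
|---|---|---|
| 30% | 0.30 × 0.56 = 16.8% | 56% |
| 60% | 0.60 × 0.56 = 33.6% | 56% |
| 90% | 0.90 × 0.56 = 50.4% | 56% |

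O/H triples with no change in what happens after referral. O/N also moves with the prevalence of hypoxaemia.

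**Step 2. Can the named proportion be recovered?**

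O/R = (O/H) / (R/H), and both terms are planned. For the middle row, 33.6% / 60% = 56%. The crude conditional proportion can therefore be obtained from planned output by one division, although the plan does not report it.

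**Step 3. Missing records**

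Keep 70% arrival and 80% oxygen use, and let a fraction u of arrivals have a usable record. Since O counts only documented oxygen, O/R = 0.70 × 0.80 × u.

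| Usable records (u) | O/R |
|---|---|
| 100% | 56% |
| 90% | 50.4% |
| 70% | 39.2% |
| 50% | 28% |

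At u = 70%, record loss alone takes 56% to 39%. With 60% referred, the plan would print O/H = 0.60 × 0.392 = 23.5%. Dividing by R/H gives 23.5% / 60% = 39.2%, not 56%. The division in step 2 repairs the denominator but not the missing records.

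The referred-and-admitted summary does not separate the two states either. SAP 6.1.1 takes hospitalisation from the caregiver's report, while oxygen comes from hospital records. A gap between admitted and oxygen given can be either non-receipt or a missing record.

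Among arrivals with a usable record, oxygen use is 80% in every row, if records are missing at random. That is a proportion of arrivals, so it supplements the proportion among referred children and does not replace it.

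**The case against.** The case on the other side has real force.

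- **Much of the cascade is already there.** SAP 6.1.5.4 summarises hypoxaemic-and-referred and hypoxaemic-referred-and-admitted children on the same denominators as oxygen. A reader might infer that the plan cannot show whether referral leads to oxygen, or that an arm with fewer referrals would pass for one whose hospitals withhold it. The documents do not support that: the referral proportion is in the same section, and step 2 recovers the crude figure. What remains is that the proportion in the outcome's title is left for the reader to derive.
- **No explicit imputation rule.** A reader might take it as a stated rule that a child without a record counts as not given oxygen. The SAP does not say so, and where it imputes elsewhere (for example SAP 6.1.2.1 and 6.1.2.6) it says so openly. The default follows only from the numerator wording and the absence of any other rule.
- **The record search is not biased at every point.** Protocol 8.2.4 seeks records for children reported to have attended hospital and for referred children lost to follow-up. Referred children reported not to have attended are left out, but on that report they received no oxygen at hospital, so nothing is missing for them. The limits that matter are the geographical restriction and the recording of oxygen only where available.
- **Size.** One might contrast 39% among referred children with 80% among those with a usable record and call the whole gap record loss. It is not: the assumed 30% who never arrive truly received none. Record loss accounts for 56% to 39%.
- **Choice of denominator.** Referral is itself affected by the intervention, so conditioning on it selects different children by arm. That is a reason to keep the all-hypoxaemic figure, not to omit the one named.
- **Reach.** The outcome has no control-arm data, India has a single intervention arm, and no stated objective compares oxygen delivery between arms or countries.

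**Conclusion.** Wrong as written, minor. Neither denominator in SAP 6.1.5.4 matches the population named in the outcome, and the section departs from the SAP's own practice for parallel outcomes. The planned proportion among hypoxaemic children moves with the referral rate: 16.8% to 50.4% as referral goes from 30% to 90%, on the assumed arrival and oxygen rates and with complete records. That part can be undone by dividing planned summaries.

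The missing-record part cannot. It rests on the implied default just described and on an assumed retrieval rate. With 70% of records usable the proportion among referred hypoxaemic children falls from 56% to 39%; over 50% to 90% usable it lies between 28% and 50.4%. The documents give no retrieval rate, so the true size is unknown.

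This is a descriptive other outcome in intervention arms only. No primary or secondary conclusion changes.

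**What to change.** In SAP 6.1.5.4:

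1. Make children with hypoxaemia referred at Day 0 the main denominator.
2. Split that group so that absence of a hospital record, or a record without oxygen status, is its own category, separate from documented non-receipt and from reported non-attendance.
3. Give oxygen use among children with a usable record as a second proportion, stating that it assumes records are missing at random.
4. Keep the all-recruited and all-hypoxaemic figures as supplements.

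The cost is a few lines of SAP wording and one table from data already planned for collection. The downside is small denominators and wide intervals.

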6.1.6 Follow-up outcomes

6.1.6.1 Proportion of children attending scheduled follow-up at the same facility by Day 7

Attendance of scheduled follow-up at the same facility will be evaluated from:

ξ Scheduled and unscheduled visits form

A child will be counted in the numerator if:

- a follow-up visit advice is recorded at Day 0 and
- a follow-up visit for the child is found in the scheduled/unscheduled visits form and
- the follow-up visit is within 7 days of Day 0 (7th day included) and conducted at the enrollment facility

All children recruited will be in the denominator.

Additionally, the proportion will be calculated and reported using only children for whom a follow-up visit advice is recorded at Day0 as denominator.

Children for whom a scheduled follow-up visit is not found in the scheduled/unscheduled visit form will be assumed to not have attended scheduled follow-up at the same facility by Day 7.

ξ Day 7 follow-up form

A child will be counted in the numerator if:

- a follow-up visit advice is recorded at Day 0 and
- the caregiver reports visiting a government / public facility (non hospital) between child's enrollment and Day 7 follow-up visit date and
- Day 7 follow-up date is within 7 days of Day 0, considering a + 3 days window (10th day included).

All children recruited will be in the denominator.

Additionally, the proportion will be calculated and reported using only children for whom a follow-up visit advice is recorded at Day0 as denominator.

Children for whom no Day7 data are available or withdrew prematurely from the study will be assumed to not have attended scheduled follow-up at the same facility / government or public facility by Day 7.

6.1.6.2 Proportion of children presenting for unscheduled follow-up to any health facility by Day 7

Attendance of unscheduled follow-up at any health facility will be evaluated from:

ξ Scheduled and unscheduled visits form

A child will be counted in the numerator if:

- a follow-up visit advice is not recorded at Day 0 and
- a follow-up visit for the child is found in the scheduled/unscheduled visits form and
- the follow-up visit is within 7 days of Day 0 (7th day included)

All children recruited will be in the denominator.

Additionally, the proportion will be calculated and reported using only children for whom a follow-up visit advice is not recorded at Day0 as denominator.

ξ Day 7 follow-up form

A child will be counted in the numerator if:

- a follow-up visit advice is not recorded at Day 0 and
- the caregiver reports visiting a health facility (any, non hospital) between child's enrollment and Day 7 follow-up visit date and
- Day 7 follow-up date is within 7 days of Day 0, considering a + 3 days window (10th day included).

All children recruited will be in the denominator.

Additionally, the proportion will be calculated and reported using only children for whom a follow-up visit advice is not recorded at Day0 as denominator.

Children for whom no Day7 data are available or withdrew prematurely from the study will be assumed to not have attended any health facility by Day 7.

6.2 Analysis Methods

6.2.1 Analytical Methods

Outcomes will be described by arm using summary statistics. In particular, counts and percentages will be used for binary variables and reported with one decimal place; mean and standard deviation (SD) or median (IQR) for continuous variables depending on their distribution. Mean and median will be displayed with one decimal place and SD and IQR will be presented with two decimal places.

The two primary outcomes will be assessed using a random effects logistic regression model with the cluster included as a random effect. If convergence issues arise due to sparse data, clusters may be dropped or combined to higher grouping level (e.g. district).

Results will be reported with odds ratios, risk differences and their associated 95% confidence intervals (CI). The control arm will be used as reference category.

Secondary outcomes and other binary outcomes of interest will be evaluated in the same way.

Other continuous outcomes of interest will be assessed using random effects linear regression model with the cluster included as a random effect. Results will be reported in terms of adjusted mean differences between arms with associated 95% CIs.

Modelling of secondary outcomes will be performed if numbers allow.

For interim analyses and DMC analyses, only the two primary outcomes will be presented. Modelling will not be performed and results will be reported in terms of summary statistics only.

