3.4 Sample Size

The sample size for the pragmatic RCT is calculated separately for each country, based on the following assumptions:

- ξ power of 80%
- ξ alpha level of 0.05 per arm
- ξ intra-cluster correlation coefficient (ICC) of 0.001
- ξ 1.1% severe complications in the control arm
- ξ 1.5% appropriate hospitalisations (within 24 hrs of Day 0 and as a results of referral) in the control arm

In India, initial sample size calculation for the three arm trial was based on having the power to detect a 30% or greater decrease in severe complication and 30% or greater increase in appropriate hospitalisation for each arm compared to control with 40 cluster per arm. This assumes average recruitment of 510 children per cluster over the 12 month period (total 40800), with an average of 110 per CHC per month and 20 children per PHC, assuming an average facility ratio CHC : PHC of 1:3. Following the decision, based on the pilot, not to introduce the CDSA, facilities were reallocated to the remaining two arms up to 60 facilities per arm.

In Tanzania, the study would have the power to detect a 30% or greater decrease in severe complication and a 30% or greater increase in appropriate hospitalisation for each arm compared to control with 22 clusters per arm. This assumes average recruitment of 1680 children per cluster over the 12 month period (total 110880), with an average of 350 children per health centre per month and 70 children per dispensary per month, assuming an average facility ratio health center : dispensary of 1:3.

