6.2.3 Test of Assumptions, Actions to be taken

Continuous variables will be inspected using histograms: 1) to assess for outliers which may be queried for accuracy, and 2) to assess whether appropriate transformations are required for analyses.

As a multilevel logistic regression model is estimated using quadrature (rather likelihood methods), a quadrature check to test for adequate model fit will be performed. In case of unreliable model fit, generalised estimating equations will be used to fit the model which will provide population-averaged odds ratios and 95% confidence intervals.

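### With 22 facilities per arm in Tanzania and no small-sample rule, default tests from the random-effects model reject modestly too often, and the uncorrected GEE fallback clearly too often

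*SAP*

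**What the plan says.** SAP 6.2.1 and Protocol 8.3.1 assess the two primary outcomes by random-effects logistic regression; the SAP describes a "random effects logistic regression model with the cluster included as a random effect". SAP 6.2.2 adjusts for the stratification factors. If the quadrature check in SAP 6.2.3 shows an unreliable fit, "generalised estimating equations will be used to fit the model which will provide population-averaged odds ratios and 95% confidence intervals".

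SAP 4.1 compares each p-value with 0.025 and allows 0.05 for severe complication once hospitalisation has been rejected. An intervention arm counts as positive if either primary outcome is positive.

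For Tanzania, SAP 3.4 bases power on each arm "compared to control with 22 clusters per arm", with "average recruitment of 1680 children per cluster over the 12 month period". That average comes from "an average of 350 children per health centre per month and 70 children per dispensary per month" and a "facility ratio health center : dispensary of 1:3".

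Neither document states whether the test is Wald or likelihood-ratio, what reference distribution applies, which working correlation a GEE would use, or whether its variance would be corrected for a limited number of clusters.

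**The concern.** Treatment varies only between facilities, so the precision of each Tanzanian comparison rests on 44 facilities, or 66 if the three arms are fitted together. With so few, normal-theory tests tend to understate uncertainty, and the uncorrected sandwich variance used by GEE is biased downward. The closed procedure in SAP 4.1 controls error only if each component test holds its own level. If the component tests do not, a 95% interval covers less than 95% and the chance of wrongly declaring an arm positive exceeds the planned 5%. The quadrature check in SAP 6.2.3 guards against numerical misfit, which is a different problem.

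**Working it through.** **1. Reproduce the plan's figure.** Inputs from SAP 3.4: 1.1% reduced by 30% to 0.77%, 80% power, "alpha level of 0.05 per arm", ICC 0.001, 1,680 children per facility.

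- n per arm without clustering = [1.96√(2p̄(1−p̄)) + 0.842√(p₁(1−p₁)+p₂(1−p₂))]² / (p₁−p₂)² = 13,351.
- Design effect = 1 + (1,680 − 1) × 0.001 = 2.679.
- Facilities = 13,351 × 2.679 / 1,680 = 21.3, so 22. Power at 22 is 81.3%.
- Hospitalisation (1.5% to 1.95%): 13,141 × 2.679 / 1,680 = 20.95, so 21.

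The stated 22 is reproduced, assuming equal facility sizes.

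**2. Facility sizes.** Health centre: 350 × 12 = 4,200. Dispensary: 70 × 12 = 840. Mean = 0.25 × 4,200 + 0.75 × 840 = 1,680. SD = √(0.25 × 0.75) × (4,200 − 840) = 1,455, a coefficient of variation (CV) of 0.87.

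**3. Random-effects model under no effect.** The simulation used 22 facilities per arm (5-6 health centres, the rest dispensaries), ICC 0.001, adjustment for facility type and location, and 15-point adaptive quadrature. There were 4,000 data sets per row. The Monte Carlo standard error is √(0.05 × 0.95 / 4,000) = 0.3 points. Degrees of freedom for t are facilities minus fixed effects: 44 − 4 = 40 pairwise, 66 − 5 = 61 joint. Each cell gives the rejection rate (%) at nominal 5% / 2.5%.

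| Scenario | Wald z | Wald t | Likelihood ratio |
|---|---|---|---|
| Tanzania, joint three-arm, 1.1% | 6.0 / 3.1 | 5.6 / 2.7 | 5.7 / 2.8 |
| Same, extra within-type CV 0.5 | 6.7 / 3.8 | 6.2 / 3.4 | 6.2 / 3.3 |
| Tanzania, pairwise, 1.1% | 7.2 / 4.2 | 6.4 / 3.5 | 6.6 / 3.6 |
| Same, extra within-type CV 0.5 | 7.1 / 4.1 | 6.5 / 3.4 | 6.6 / 3.4 |
| Pairwise, 1.5%, within-type CV 0.5 | 7.1 / 3.9 | 6.3 / 3.3 | 6.3 / 3.3 |
| Pairwise, 1.1%, all facilities 1,680 | 6.6 / 3.6 | 5.8 / 2.9 | 5.9 / 3.0 |
| India, 60 per arm, 1.1% | 5.5 / 2.5 | 5.3 / 2.4 | 5.4 / 2.5 |

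A second simulation (3,000 data sets, adjusted for facility type only) gave 6.6-6.8% and 3.8-4.3% for Wald z, and 6.0-6.2% and 3.1-3.6% with t on 41 degrees of freedom.

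**4. GEE under no effect.** Tanzania, 10,000 data sets per scenario, Monte Carlo standard error about 0.2 points.

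| GEE variant | Nominal 5% | Nominal 2.5% |
|---|---|---|
| Exchangeable, uncorrected, z | 7.2-8.6 | 4.1-5.1 |
| Independence, uncorrected, z | 9.1-11.2 | 5.6-7.4 |
| Exchangeable, Kauermann-Carroll, t | 5.5-6.2 | 2.8-3.3 |
| Exchangeable, Mancl-DeRouen, t | 4.4-4.8 | 2.2-2.6 |

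With equal facility sizes the uncorrected GEE rate is 7.0% at nominal 5%. In India it is 6.2% (exchangeable) and 6.5% (independence).

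The second simulation gave 7.9-8.9% and 4.7-5.4% for uncorrected independence GEE, and 4.9% and 2.7% with Mancl-DeRouen and t. The independence figure therefore depends on simulation choices; its direction does not.

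**5. Effect on the SAP 4.1 procedure.** The first step rejects if either p-value is at most 0.025. If the outcomes are independent, the nominal chance is 1 − 0.975² = 4.9%. Simulated for one Tanzanian intervention-control comparison (3,000 runs): 7.7-9.0% with random-effects Wald, 9.7-10.3% with exchangeable GEE, 11.2-15.4% with independence GEE.

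**The case against.** The SAP never says Wald. A reader might infer that it chose an uncorrected Wald test, but the documents are silent, and silence is not that choice. This stands, and Wald is treated here as an inference about default output. The silence still matters, because a plain likelihood-ratio test also runs above nominal (5.7-6.6% and 2.8-3.6%).

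A reader might also blame the five-fold spread in facility size for the random-effects excess. The calculations do not support that: equal sizes still give 6.6%, against 7.1-7.2% pairwise with unequal sizes. Few clusters account for most of it. Unequal sizes matter mainly for GEE.

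It is also fair to say that the primary-model excess is modest. SAP 6.2.1 takes control as the reference category, which fits a joint 66-facility model at least as well as separate pairwise fits. The joint fit gives 6.0-6.7%, against 7.1-7.2% pairwise. Calling the rate well above 0.025 suits the GEE results better than the planned model.

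Finally, GEE is a contingency, used only after a failed fit check. That limits how likely its figures are to apply. It does not excuse leaving the fallback uncorrected, since it is written into the plan and would be used exactly when the primary fit is in doubt.

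**Conclusion.** The point holds for Tanzania. Default inference from the random-effects model exceeds its level by about 1 to 2 points at 5% and 0.6 to 1.7 points at 2.5% (3.1-4.2%). Uncorrected GEE exceeds it by roughly 2 to 4 points (exchangeable) or 4 to 6 points (independence) at 5%.

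The plan's rates, ICC, facility counts and mean sizes were used throughout. The within-type CV of 0.5, the balanced location split, the GEE working correlations and the independence of the two outcomes in step 5 are assumptions. At assumed ICCs of 0.005-0.01, the rates at nominal 5% are 6.0-6.7% for random effects, 8.0-8.5% for exchangeable GEE and 12.6-13.6% for independence GEE.

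A reader might extend the finding to India or to the pooled analysis. The Indian random-effects result is close to nominal, and the pooled analysis was not simulated. The SAP 6.2.1 option of merging clusters to a higher level was not simulated either; it would leave very few clusters.

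**What to change.** - **SAP 6.2.3:** for any GEE, state the working correlation and require Mancl-DeRouen-type standard errors with a t reference on cluster-level degrees of freedom. With exchangeable correlation this gives about 4-5% at nominal 5% and 2-3% at nominal 2.5%.
- **SAP 6.2.1:** name the test, say whether the Tanzanian arms are fitted jointly or in pairs, and use t with cluster-level degrees of freedom. Record that t only partly removes the excess (5.6-6.5% and 2.7-3.5% in step 3).
- **Permutation test:** pre-specify one over facilities within randomisation strata. It must use the randomised allocation, because SAP 4.3 analyses some facilities by the package they delivered, which would break the basis for permuting. It was not simulated here; its validity rests on following the actual stratified allocation.
- **SAP 4.1:** state in advance which p-value is compared with 0.025 and 0.05, so that disagreement between methods cannot be settled after the results are seen.

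This needs SAP wording and standard analysis methods, with no new data. Intervals widen slightly and power falls slightly. The power margin is thin: 81.3% at 22 facilities per arm, at alpha 0.05 and with equal sizes.
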